**EFS specific**

Table 65: Event Free Survival specific

EFS (event)	N	%	95%CI
Event/Death			
No			
Total			

Table 66: Type of event: EFS specific

(N=)
Type of event: EFS specific
No
Bladder relapse/Metastases
Bladder relapse
Metastases
Death

Table 67: Survival Median/Mean EFS specific

	Median	95%CI	Mean	95%CI
EFS				

#### 3.12.1. EFS SPECIFIC ESTIMATED AT 6, 12, 18 AND 24 MONTHS (KAPLAN-MEIER)

Table 68: EFS specific at 6, 12, 18 and 24 months

EFS specific	Events (% total N)	Patients at risk	% estimated cumulative survival ratio	95% IC
At 6 months				
At 12 months				
At 18 months				
At 24 months				

Note: Estimated using Kaplan-Meier product-limit method

### 3.12.1.1. FIGURE: EFS SPECIFIC

#### List of patients. Events: EFS specific

Table 69: List of patients. EFS specific

Patient ID	Hospital	Event EFS specific	Date EFS specific

### 3.13. SECONDARY OBJECTIVE 1E: PFS (TUMOUR ASSESSMENT)

Time from treatment start to tumour relapse or distant progression (or death)

#### PFS Tumour assessment

Table 70: PFS Tumour Assessment

EFS (event)	N	%	95%CI
PD/Death			
Alive			
Total			

Table 71: Type of event: PFS Tumour assessment

(N=)
Type of event: PFS Tumour assessment
Alive without PD
PD (tumour assessment)
Death

Table 72: Survival Median/Mean PFS Tumour assessment

	Median	95%CI	Mean	95%CI
PFS				

#### 3.13.1. PFS TUMOUR ASSESSMENT ESTIMATED AT 6, 12, 18 AND 24 MONTHS (KAPLAN-MEIER)

Table 73: PFS Tumour assessment at 6, 12, 18 and 24 months

PFS Tumour assessment	Events (% total N)	Patients at risk	% estimated cumulative survival ratio	95% IC
At 6 months				
At 12 months				
At 18 months				
At 24 months				

Note: Estimated using Kaplan-Meier product-limit method

### 3.13.1.1. FIGURE: PFS TUMOUR ASSESSMENT

#### List of patients. Events: PFS Tumour assessment

Table 74: List of patients. PFS

Patient ID	Hospital	Event PFS	Date PFS

### 3.14. SECONDARY OBJECTIVE 1F: OVERALL SURVIVAL

Time from treatment start to Death.

#### Overall Survival

Table 75: Overall Survival

EFS (event)	N	%	95%CI
Death			
Alive			
Total			

Table 76: Type of event: Overall Survival

(N=)	
Type of event: Overall Survival	
Alive at end of trial: Patient's decision	
Alive at end of trial according to protocol	
Death	

Table 77: Overall Survival Median/Mean

	Median	95%CI	Mean	95%CI
OS				

### 3.14.1. OS ESTIMATED AT 6, 12, 18 AND 24 MONTHS (KAPLAN-MEIER)

Table 78: Overall Survival at 6, 12, 18 and 24 months

OS	Events (%, total N)	Patients at risk	% estimated cumulative survival ratio	95% IC
At 6 months				

OS	Events (% total N)	Patients at risk	% estimated cumulative survival ratio	95% IC
At 12 months				
At 18 months				
At 24 months				

Note: Estimated using Kaplan-Meier product-limit method

### 3.14.1.1. FIGURE: OVERALL SURVIVAL

Table 79: Details of deaths

Patient ID	Hospital	Status	Death Reason

### 3.15. SECONDARY OBJECTIVE: EFS MUSCLE INVASIVE

Muscle invasive events (bladder relapse) recorded in follow-up bladder disease section of the eCRD.

Table 80: EFS: Muscle invasive (patients with cystoscopy)

Muscle invasive (event)	N	%	95%CI
No			
Yes			
Total			

Table 81: Survival Median/Mean EFS Muscle Invasive

	Median	95%CI	Mean	95%CI
EFS				

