- At 30 minutes during the infusion ( $\pm 5$  minutes)
- At the end of the infusion (at 60 minutes  $\pm 5$  minutes)
- In the 1-hour observation period post-infusion: 30 and 60 minutes after the infusion (i.e., 90 and 120 minutes from the start of the infusion) ( $\pm 5$  minutes) – for the first infusion only and then for subsequent infusions as clinically indicated

If the infusion takes longer than 60 minutes, then blood pressure and pulse measurements should follow the principles as described above or more frequently if clinically indicated.

d ECG during screening and on cycle 1 Day 1 within 1 hr prior to the start of the first study treatment. Thereafter as clinically indicated.

e According what is detailed on tables 4 and 5. If screening laboratory assessments are performed within 3 days prior to Day 1 they do not need to be repeated at Day 1. Results for safety bloods must be available and reviewed before commencing an infusion. Gamma glutamyltransferase tested at Screening, Day 1 and as clinically indicated. Depending on the profile of the combination agent, the frequency of the hematology, serum chemistry and LFT testing may need to be increased to every two weeks.

f Free T3 and free T4 will only be measured if TSH is abnormal. They should also be measured if there is clinical suspicion of an adverse event related to the endocrine system.

g Urinalysis performed at Screening, Day 1, every 4 weeks and as clinically indicated.

h Coagulation tests: prothrombin time, APTT and INR – to be performed at screening and EoT visit, and only as clinically indicated thereafter.

i Timing of CT scans:

- Initial Staging: thorax, abdomen and pelvis CT scan
- Post-therapy re-staging (week 12): thorax, abdomen and when applicable pelvis CT scan

j Six weeks since the end of radiotherapy. Cystoscopy and bladder biopsy will be performed for ALL patients as an efficacy determination

k Follow-up: Pelvis and abdomen CT scan, urine cytology and Rx Thorax every 3 months the first year, every 4 months the second year and every 6 months thereafter. Additional cystoscopy and bladder biopsy will be performed in case of detection abnormalities in the cytology or imaging studies

l Peripheral blood: Week 1 prior to the administration of durvalumab and tremelimumab, W2 before initiation of RT, W8 at the end of RT, and W12 at the time of tumor response

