Patients will be followed up every 3 months the first year, every 4 months the second year and every 6 months thereafter with abdomen and pelvis CT scan, Rx thorax, urine cytology. Additional cystoscopy and bladder biopsy will be performed anytime in case of detection abnormalities in the cytology or imaging studies. The study will be closed 2 years after the last patient inclusion.

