#### List of patients without Cystoscopy

Table 45: List of patients without Cystoscopy

Patient ID	Hospital	Cystoscopy done	Reason Cystoscopy not done	Death Reason

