#### 3.15.1.1. FIGURE: EFS MUSCLE INVASIVE

Table 83: List of patients with EFS Muscle Invasive

Patient Number	Hospital	Response evaluation at 6w after RDT: Muscle-invasive bladder cancer	Muscle invasive (patients with cystoscopy - bladder disease FU)	Date Muscle invasive	Non-Muscle invasive (patients with cystoscopy - bladder disease FU)	Date Non-Muscle invasive FU)	Response evaluation: Non-Invasive bladder cancer (including Muscle invasive)

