### 3.16. SECONDARY OBJECTIVE: EFS NON MUSCLE INVASIVE

Non-muscle invasive events (bladder relapse) recorded in follow-up bladder disease section of the eCRD.

Table 84: EFS: Non-Muscle invasive (patients with cystoscopy)

Non-Muscle invasive (event)	N	%	95%CI
No			
Yes			
Total			

Table 85: Survival Median/Mean EFS NON MUSCLE Invasive

	Median	95%CI	Mean	95%CI
EFS				

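### The relapse count tables in SAP 3.15 and 3.16 are limited by title to patients with cystoscopy, a set selected after baseline and in conflict with the SAP's all-32 population

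*Combined protocol and SAP*

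**What the plan says.** SAP 3.15 takes its events from follow-up: "Muscle invasive events (bladder relapse) recorded in follow-up bladder disease section of the eCRD". SAP 3.16 does the same for non-muscle-invasive relapse. The two count tables are titled "Table 80: EFS: Muscle invasive (patients with cystoscopy" and "Table 84: EFS: Non-Muscle invasive (patients with cystoscopy". Each has only the rows No, Yes and Total, with a percentage and a 95% confidence interval.

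Neither section says which cystoscopy is meant. The listing in Table 83 has a column headed "Muscle invasive (patients with cystoscopy - bladder disease FU", and Table 87 repeats it.

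The protocol has two kinds of post-treatment cystoscopy:

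- **Response cystoscopy**, six weeks after radiotherapy and mandatory: "Cystoscopy and bladder biopsy will be performed for ALL patients as an efficacy determination" (schedule footnote j).
- **Follow-up cystoscopy**, which is triggered: "Additional cystoscopy and bladder biopsy will be performed anytime in case of detection abnormalities in the cytology or imaging studies" (protocol 3.1; also protocol 6 and schedule footnote k). The version of footnote k in protocol 3.2 adds symptoms as a trigger.

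The SAP allows for patients who never reach the response cystoscopy: "Table 45: List of patients without Cystoscopy" has a column for reason of death. SAP 3.1 says that all efficacy and safety analyses use the Safety population, because all 32 patients qualify for every set.

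**The concern.** Whether a patient has a follow-up cystoscopy depends on what happens after treatment starts. Under the protocol, it means that cytology, imaging or symptoms already raised suspicion. A relapse proportion among those patients answers a different question from the proportion of treated patients who relapse, and it would normally be higher.

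The wording also leaves the programmer with two instructions that cannot both be followed: the table titles and SAP 3.1. Nothing says which prevails. These two tables help to describe how durable bladder preservation is, so a reader could take a rate among suspected patients for a rate among treated patients.

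**Working it through.** The plan states no rate, event count or denominator for 3.15 or 3.16, so there is no figure to reproduce. The check compares the passages and then illustrates the effect of the denominator.

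**1. Is the restriction more than a loose title?** Tables 46 to 48 keep unscoped patients in the total through a row for cystoscopy not done. Table 57 keeps deaths in a row of their own. Tables 80 and 84 have neither row. The parallel count table for metastases (Table 88) carries no cystoscopy phrase. As printed, Tables 80 and 84 have no place for an unscoped patient or for a death without relapse.

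**2. Which cystoscopy?** The event source and the listing columns both point to follow-up. The response cystoscopy remains a possible reading, because the titles do not say.

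**3. Effect on the proportion.** Let e be the number of relapses and m the number in the set. The proportion is e/m. Assume that every counted relapse was confirmed at a cystoscopy, so that e stays fixed. A smaller m can then only raise e/m. Intervals are exact (Clopper-Pearson) 95%. The values of e and all values of m below 32 are assumptions.

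| Set | m | e = 3 | e = 5 (95% CI) | e = 8 |
|---|---|---|---|---|
| All treated | 32 | 9.4% | 15.6% (5.3 to 32.8) | 25.0% |
| Response cystoscopy done, 4 missing | 28 | 10.7% | 17.9% (6.1 to 36.9) | 28.6% |
| Triggered follow-up cystoscopy in 12 | 12 | 25.0% | 41.7% (15.2 to 72.3) | 66.7% |

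If three to six patients lack the response cystoscopy, m runs from 32 - 3 = 29 to 32 - 6 = 26. Five relapses then give 5/29 = 17.2% to 5/26 = 19.2%. If 20 or 16 patients had a triggered cystoscopy instead of 12, five relapses give 5/20 = 25.0% or 5/16 = 31.2%.

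**4. How far does the restriction reach?** Tables 81 and 82 (muscle-invasive) and 85 and 86 (non-muscle-invasive) give the Kaplan-Meier medians, means and time-point estimates. None prints the cystoscopy phrase. Tables 82 and 86 express events as a percentage of a total N that is not stated. SAP 3.18 gives cumulative incidences for the same relapse types, with death and cystectomy among the competing events, and prints no restriction and no N.

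**The case against.** The strongest reply is that SAP 3.1 governs: every efficacy analysis uses all 32 patients, so the phrase may be only a label. The SAP is a set of output shells that elsewhere prints raw variable names as headings, and this phrase could be a data-source label carried over. That is possible, and it means the restriction is not a settled rule. It does not remove the conflict, because the tables as titled and laid out have no place for unscoped patients.

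A second reply is that the response cystoscopy is mandatory. If that is the one meant, the set is close to all 32 and the shift is small beside the width of the interval. This stands for that reading, but the listings point to the other one.

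A third is that 3.15 and 3.16 are additional analyses, absent from Table 8 of the protocol, and that the primary endpoint is untouched. This also stands, and it limits the importance of the point.

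A reader might infer more than the documents support:

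- **That the survival curves are restricted too.** The Kaplan-Meier tables do not say so.
- **That patients kept in the set gain guaranteed event-free time** up to the response cystoscopy, about 2 + 32/5 + 6 = 14.4 weeks after treatment start. Events here come only from the follow-up section, and death is not a row in Tables 80 or 84. If death is censored, patients who die before the response cystoscopy leave before the first possible event. They enter no Kaplan-Meier factor, and dropping them leaves the curve unchanged.
- **That 3.18 or the bladder-preservation endpoint in 3.11 reports the same quantity on another denominator.** SAP 3.18 prints no N and estimates a competing-risk quantity. The 3.11 endpoint is a composite that also counts metastasis, cystectomy and death.
- **That the relapse rate will be reported as 42% instead of 16%.** That contrast needs an assumed 12 scoped patients and one of two readings.

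**Conclusion.** The point holds for the two count tables. Taken at their titles, Tables 80 and 84 compute a relapse proportion and its interval in a set chosen by post-baseline events, most naturally those with a follow-up cystoscopy triggered by suspicion. This contradicts SAP 3.1.

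The direction is upward for any fixed number of confirmed relapses. The size is unknown, because the documents give neither the number of relapses nor the number scoped. For five relapses the range runs from almost no change on the response-cystoscopy reading to more than a doubling on the follow-up reading with 12 scoped. Bias in the Kaplan-Meier estimates is not shown. The sponsor should correct the tables, although the primary analysis does not depend on them.

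**What to change.** - In Tables 80 and 84, delete the restriction and report all 32 treated patients. Use separate rows for relapse, no relapse, death without relapse and response cystoscopy not done, following Tables 46 and 57. State an order of precedence so that each patient falls in one row. Simply moving to a Yes/No table on 32 would count early deaths and never-scoped patients as relapse-free.
- Give the number of patients with a follow-up cystoscopy as a descriptive line.
- State that Tables 81, 82, 85 and 86 use the same 32 patients, with time from treatment start.
- Name the cumulative incidence in SAP 3.18 as the main relapse estimate, since it handles death and cystectomy as competing events.

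The cost is one population flag, revised titles and rows, and a sentence or two of text. No new data are needed, and patient care does not change.

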#### 3.15.1. EFS MUSCLE INVASIVE ESTIMATED AT 6, 12, 18 AND 24 MONTHS (KAPLAN-MEIER)

Table 82: EFS Muscle Invasive at 6, 12, 18 and 24 months

EFS Muscle Invasive	Events (% total N)	Patients at risk	% estimated cumulative survival ratio	95% IC
At 6 months				
At 12 months				
At 18 months				
At 24 months				

Note: Estimated using Kaplan-Meier product-limit method

#### 3.15.1.1. FIGURE: EFS MUSCLE INVASIVE

Table 83: List of patients with EFS Muscle Invasive

Patient Number	Hospital	Response evaluation at 6w after RDT: Muscle-invasive bladder cancer	Muscle invasive (patients with cystoscopy - bladder disease FU)	Date Muscle invasive	Non-Muscle invasive (patients with cystoscopy - bladder disease FU)	Date Non-Muscle invasive FU)	Response evaluation: Non-Invasive bladder cancer (including Muscle invasive)

### 3.16. SECONDARY OBJECTIVE: EFS NON MUSCLE INVASIVE

Non-muscle invasive events (bladder relapse) recorded in follow-up bladder disease section of the eCRD.

Table 84: EFS: Non-Muscle invasive (patients with cystoscopy)

Non-Muscle invasive (event)	N	%	95%CI
No			
Yes			
Total			

Table 85: Survival Median/Mean EFS NON MUSCLE Invasive

	Median	95%CI	Mean	95%CI
EFS				

#### 3.16.1. EFS NON MUSCLE INVASIVE ESTIMATED AT 6, 12, 18 AND 24 MONTHS (KAPLAN-MEIER)

Table 86: EFS Non-Muscle invasive at 6, 12, 18 and 24 months

EFS NON MUSCLE Invasive	Events (% total N)	Patients at risk	% estimated cumulative survival ratio	95% IC
At 6 months				
At 12 months				
At 18 months				
At 24 months				

Note: Estimated using Kaplan-Meier product-limit method

#### 3.16.1.1. FIGURE: EFS NON MUSCLE INVASIVE

Table 87: List of patients with EFS Non-Muscle Invasive

Patient Number	Hospital	Response evaluation at 6w after RDT: Muscle-invasive bladder cancer	Muscle invasive (patients with cystoscopy - bladder disease FU)	Date Muscle invasive	Non-Muscle invasive (patients with cystoscopy - bladder disease FU)	Date Non-Muscle invasive	Response evaluation: Non-Invasive bladder cancer (including Muscle invasive)

### 3.17. SECONDARY OBJECTIVE: METASTASES

Metastases events recorded in follow-up metastases section of the eCRD.

Table 88: EFS: Metastases

Metastases (event, includes death due to PD)	N	%	95%CI
Yes			
No			
Total			

Table 89: Survival Median/Mean EFS METASTASES

	Median	95%CI	Mean	95%CI
EFS				

#### 3.17.1. EFS METASTASES ESTIMATED AT 6, 12, 18 AND 24 MONTHS (KAPLAN-MEIER)

Table 90: EFS METASTASES at 6, 12, 18 and 24 months

EFS METASTASES	Events (% total N)	Patients at risk	% estimated cumulative survival ratio	95% IC
At 6 months				
At 12 months				
At 18 months				
At 24 months				

Note: Estimated using Kaplan-Meier product-limit method

#### 3.17.1.1. FIGURE: EFS METASTASES

Table 91: List of patients with EFS Metastases

Patient Number	Hospital	Response evaluation at 6w after RDT: Muscle-invasive bladder cancer	Muscle invasive (patients with cystoscopy - bladder disease FU)	Date Muscle invasive	Non-Muscle invasive (patients with cystoscopy - bladder disease FU)	Date Non-Muscle invasive	Response evaluation: Non-Invasive bladder cancer (including Muscle invasive)

### 3.18. ESTIMATION OF CUMULATIVE INCIDENCE (COMPETING RISKS ANALYSIS)

#### 3.18.1. CIF: MUSCLE INVASIVE BLADDER CANCER

In this section the event of interest was the relapse due to the presence of **muscle invasive bladder cancer** and the cumulative incidence is estimated in the presence of the following competitive events:

- *Death*
- *Cystectomy*

Table 92: Muscle Invasive Bladder Cancer and competitive events

(N=)
Events (Muscle Invasive Bladder Cancer)
Event=Death
Event=Muscle Invasive Bladder Cancer
No

Table 93: List of patients with cumulative event: muscle invasive bladder cancer

Patient Number	Date treatment initiation	Events (Muscle Invasive Bladder Cancer)	Date Event/Follow-up	Time from treatment initiation	Cytoscopy	Exitus Reason	Last available date	Late salvage cystectomy date

Table 94: Cumulative Incidence of Muscle Invasive Bladder Cancer (in the presence of competitive events)

Time	Estimated Cumulative Incidence (95% CI)
6 months	
12 months	
18 months	
24 months	
36 months	

##### 3.18.1.1. FIGURE: CIF MUSCLE INVASIVE BLADDER CANCER AND COMPETITIVE EVENTS

### 3.18.2. CIF: MUSCLE NON INVASIVE BLADDER CANCER

In this section the event of interest was the relapse due to the presence of **muscle non invasive bladder cancer** and the cumulative incidence is estimated in the presence of the following competitive events:

- *Death*
- *Cystectomy*
- *Muscle Invasive Bladder Cancer*

Table 95: Muscle Non Invasive Bladder Cancer and competitive events

(N=)	
Events (Muscle Non Invasive Bladder Cancer)	
Event=Death	
Event=Muscle Invasive Bladder Cancer	
Event=Muscle Non Invasive Bladder Cancer	
No	

Table 96: List of patients with cumulative event: Non-invasive muscle bladder cancer

Patient Number	Date treatment initiation	Events (Muscle Non Invasive Bladder Cancer)	Date Event/Follow -up	Time from treatment initiation	Cytoscopy	Exitus Reason	Last available date	Late salvage cystectomy date

Table 97: Cumulative Incidence of Muscle Non Invasive Bladder Cancer (in the presence of competitive events)

Time	Estimated Cumulative Incidence (95% CI)
6 months	
12 months	
18 months	
24 months	
36 months	

#### 3.18.2.1. FIGURE: CIF MUSCLE NON INVASIVE BLADDER CANCER AND COMPETITIVE EVENTS

### 3.18.3. CIF: RELAPSE BLADDER CANCER

In this section the event of interest was the **relapse bladder cancer** and the cumulative incidence is estimated in the presence of the following competitive events:

- *Death*
- *Cystectomy*

Table 98: Relapse Bladder Cancer and competitive events

(N=)
Events (Any Bladder Cancer)
Event= Any Bladder Cancer
Event=Death
No

Table 99: List of patients with cumulative event: Bladder cancer (Any type)

Patient Number	Date treatment initiation	Events (Any Bladder Cancer)	Date Event/Follow -up	Time from treatment initiation	Cytoscopy	Exitus Reason	Last available date	Late salvage cystectomy date

Table 100: Cumulative Incidence of Relapse Bladder Cancer (in the presence of competitive events)

Time	Estimated Cumulative Incidence (95% CI)
6 months	
12 months	
18 months	
24 months	
36 months	

#### 3.18.3.1. FIGURE: CIF RELAPSE BLADDER CANCER AND COMPETITIVE EVENTS

### 3.18.4. CIF: METASTASES

In this section the event of interest was the **Metastases** and the cumulative incidence is estimated in the presence of the following competitive events:

- *Death*

Table 101: Metastases and competitive events

	(N=)
Events (Metastases)	
Event = Metastases	
Event=Death	
No	

Table 102: Cumulative Incidence of Metastases (in the presence of competitive events)

Time	Estimated Cumulative Incidence (95% CI)
6 months	
12 months	
18 months	
24 months	
36 months	

#### 3.18.4.1. FIGURE: CIF METASTASES AND COMPETITIVE EVENTS

## 4. PROGNOSIS FACTORS FOR EFS BLADDER PRESERVATION, EFS (SPECIFIC), PFS AND OS

### 4.1. EFS BLADDER PRESERVATION

#### 4.1.1. AGE

Table 103: EFS bladder preservation by age

Age at start of treatment	Age < 71 (N=)	Age ≥ 71 (N=)	Total (N=)	p value
Event Free Survival bladder preserved				
No				
Late salvage cystectomy/Bladder relapse				
Bladder relapse/Metastases				
Bladder relapse				
Metastases				
Death				
Event Free Survival bladder preserved				
Event/Death				
No				
1. Fisher's Exact Test for Count Data				
2. Pearson's Chi-squared test				

Table 104: Median/mean EFS bladder preservation by age (estimated by Kaplan-Meier)

	Median (months)	CI 95%	Mean	CI 95%
Age < 71				
Age ≥ 71				

Table 105: EFS bladder preservation by age estimated survival ratio

EFS bladder preservation	Events (% total N)	Patients at risk	% estimated cumulative survival ratio	CI 95%
Age < 71				
At 6 months				
At 12 months				
At 24 months				
At 36 months				
Age ≥ 71				
At 6 months				
At 12 months				
At 24 months				
At 36 months				

4.1.1.1. FIGURE: EFS BLADDER PRESERVATION VS AGE (ABOVE OR BELOW 71)

#### 4.1.2. GENDER

Table 106: EFS bladder preservation by gender

Sex	Female (N=)	Male (N=)	Total (N=)	p value
Event Free Survival bladder preserved				
No				
Late salvage cystectomy/Bladder relapse				
Bladder relapse/Metastases				
Bladder relapse				
Metastases				
Death				
Event Free Survival bladder preserved				
Event/Death				
No				

1. Fisher's Exact Test for Count Data

Table 107: Median/mean EFS bladder preservation by gender (estimated by Kaplan-Meier)

	Median (months)	CI 95%	Mean	CI 95%
Female				
Male				

Table 108: EFS bladder preservation by gender estimated survival ratio

EFS bladder preservation	Events (% total N)	Patients at risk	% estimated cumulative survival ratio	CI 95%
Female				
At 6 months				
At 12 months				
At 24 months				
At 36 months				
Male				
At 6 months				
At 12 months				
At 24 months				
At 36 months				

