## 3. RESULTS

### 3.1. POPULATION AND RECRUITED PATIENTS

#### Analysis Population Definitions

All efficacy and safety analyses will be performed using the Safety population because all the patients (n = 32) fulfil the conditions to be included in the safety and efficacy (PP) populations, which include all patients who received at least 2 doses of Durvalumab and at least 3 weeks of radiotherapy.

Table 4: Populations and Hospital

(N=)	
Safety analysis set	Yes
Intention to treat population	Yes
Per protocol population	Yes
Hospital	

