#### 4.1.6.1. FIGURE: EFS BLADDER PRESERVATION VS PD-L1: HIGH vs. Low/NEGATIVE

#### 4.1.7. CREATININE CLEARANCE: < 60 vs $\geq$ 60 (mL/min)

Table 121: EFS bladder preservation by Creatinine clearance: < 60 vs  $\geq$  60 (mL/min)

Creatinine clearance (mL/min)	< 60 (N=)	$\geq$ 60 (N=)	Total (N=)	p value
Event Free Survival bladder preserved				
No				
Late salvage cystectomy/Bladder relapse				
Bladder relapse/Metastases				
Bladder relapse				
Metastases				
Death				
Event Free Survival bladder preserved				
Event/Death				
No				
1. Fisher's Exact Test for Count Data				

Table 122: Median/mean EFS bladder preservation by Creatinine clearance: < 60 vs  $\geq$  60 (mL/min) (estimated by Kaplan-Meier)

	Median (months)	CI 95%	Mean	CI 95%
< 60				
$\geq$ 60				

Table 123: EFS bladder preservation by Creatinine clearance: < 60 vs  $\geq$  60 (mL/min) estimated survival ratio

EFS bladder preservation	Events (% total N)	Patients at risk	% estimated cumulative survival ratio	CI 95%
< 60				
At 6 months				
At 12 months				
At 24 months				
At 36 months				
$\geq$ 60				
At 6 months				
At 12 months				
At 24 months				
At 36 months				

**4.1.7.1. FIGURE: EFS BLADDER PRESERVATION VS CREATININE CLEARANCE:  
 $< 60$  vs  $\geq 60$  (mL/min)**

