## 1.1. EFS BLADDER PRESERVATION UNIVARIATE AND MULTIVARIATE COX MODEL

Table 124: EFS bladder preservation univariate and multivariate Cox model

	Univariate Cox Regression				Multivariate Cox Regression				Multivariate Cox Regression (Excluding PD-L1)						
	N	Event	NHR 	95% CI 	p-value	N	Event	NHR 	95% CI 	p-value	N	Event	NHR 	95% CI 	p-value
Age at start of treatment															
Age < 71															
Age ≥ 71															
Sex															
Female															
Male															
T Stage															
T2															
T3/T4															
ECOG															
0															
1															
Non Invasive Cancer History															
Yes															
No															
PD-L1 High status															
Low/Negative															
High															
Creatinine clearance															
< 60															
≥ 60															

HR = Hazard Ratio, CI = Confidence Interval; Wald test

1.1.1.1.

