**FIGURE: FOREST PLOT EFS BLADDER PRESERVATION UNIVARIATE COX MODEL**

Table 125: Creatinine clearance and ECOG contingency table, only patients with EFS bladder preservation

Creatinine clearance (mL/min)	< 60 (N=)	≥ 60 (N=)	Total (N=)	p value
ECOG				
0				
1				

1. Fisher's Exact Test for Count Data

Table 126: Creatinine clearance and ECOG contingency table, only patients without EFS bladder preservation

Creatinine clearance (mL/min)	< 60 (N=)	≥ 60 (N=)	Total (N=)	p value
ECOG				
0				
1				

1. Fisher's Exact Test for Count Data

Table 127: EFS bladder preservation multivariate model

Characteristic	Multivariate Cox Regression					Multivariate Cox Regression (Excluding PD-L1)				
	N	Event N	HR 	95% CI 	p-value	N	Event N	HR 	95% CI 	p-value
Sex										
Female										
Male										
T Stage										
T2										
T3/T4										
ECOG										
0										
1										
Non Invasive Cancer										
History										
Yes										
No										
PD-L1 High status										
Low/Negative										
High										

HR = Hazard Ratio, CI = Confidence Interval

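### Age and creatinine clearance enter every Cox model only as unexplained two-group splits, although both are collected as continuous values; creatinine clearance by ECOG is tabulated only within outcome groups

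*Combined protocol and SAP*

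**What the plan says.** SAP section 4 examines seven factors for EFS bladder preservation, EFS (specific), PFS and OS. Section numbering restarts partway through the SAP body, so table numbers are the safer reference.

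- **Age** is shown by group, for example "FIGURE: EFS BLADDER PRESERVATION VS AGE (ABOVE OR BELOW 71".
- **Creatinine clearance** is shown the same way. Table 121 is titled "EFS bladder preservation by Creatinine clearance: < 60 vs" ≥ 60 mL/min.
- **Cox models.** Table 124, under "EFS BLADDER PRESERVATION UNIVARIATE AND MULTIVARIATE COX MODEL", lists age only as < 71 and ≥ 71 and clearance only as < 60 and ≥ 60. Tables 149, 173 and 197 repeat this for the other three endpoints. No continuous term appears.
- **Form of the data.** Tables 5 and 18 summarise age and clearance with mean, SD, median and range, so both are held as numbers.
- **Creatinine clearance by ECOG.** After the Table 124 models come "Table 125: Creatinine clearance and ECOG contingency table, only patients with EFS bladder preservation" and "Table 126: Creatinine clearance and ECOG contingency table, only patients without EFS bladder preservation", each with a Fisher exact p value. Tables 150/151 and 174/175 do the same for EFS (specific) and PFS. OS has no such pair, and no table covers all patients.
- **Patients.** SAP section 3.1 uses a single population "because all the patients (n = 32) fulfil the conditions to be included in the safety and efficacy (PP) populations".

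No reason is given for either cut-off, and no purpose for the paired tables. Protocol Table 8 plans Kaplan-Meier estimation only for the survival endpoints. The clinical factors it names for the logistic models do not include age or clearance.

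**The concern.** With 32 patients, a prognostic analysis has little information to spare. Cutting a measured variable in two treats everyone on one side of the cut as identical and patients just either side of it as different. It lowers power and ties the hazard ratio to the chosen cut, and it saves nothing, because a linear term also costs one degree of freedom.

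The paired creatinine-ECOG tables raise a separate question. Whether two baseline factors overlap is a question about all patients at baseline. Splitting by outcome first conditions on something both factors may influence, and leaves each test with only part of the 32 patients.

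What is at stake is the precision and readability of an exploratory section, not the trial's main conclusion.

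**Working it through.** **Plan figure.** The total is 12 + 20 = 32 (protocol section 11.3), matching SAP section 3.1. The documents give no event number, power or information figure for the prognostic section, so there is nothing further to reproduce.

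**Step 1: information kept by a split.** For a covariate cut so that a fraction p lies on one side:

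- Normal covariate: φ(z_p)² / [p(1 − p)].
  - p = 0.5: 0.3989² / 0.25 = 0.637, so 36% is lost.
  - p = 0.3: 0.576 kept, 42% lost.
  - p = 0.2: 0.2800² / 0.16 = 0.490 kept, 51% lost.
  - p = 0.1: 0.342 kept, 66% lost.
- Uniform covariate: 3p(1 − p). At p = 0.5 this is 0.75, so 25% is lost.

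**Step 2: effect on power.** Approximate power for one covariate, two-sided 5%, is Φ(ln HR × √(events × e) − 1.96), where e is the information kept and HR is per SD. Event counts are assumed; the normal covariate is as in step 1.

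| Events (assumed) | HR per SD | Continuous | Median split | 20/80 split |
|---|---|---|---|---|
| 8 | 2.0 | 50% | 35% | 28% |
| 12 | 1.5 | 29% | 20% | 16% |
| 12 | 2.0 | 67% | 48% | 39% |
| 20 | 2.0 | 87% | 70% | 58% |

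For example, with 12 events and HR 2.0: 0.693 × √12 = 2.40, and 2.40 − 1.96 = 0.44, giving 67%. With e = 0.637: 2.40 × 0.798 = 1.92, and 1.92 − 1.96 = −0.04, giving 48%.

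**Step 3: creatinine-ECOG odds ratio within outcome groups.** Take two independent binary factors with hazard ratios h1 and h2, and event-free probability s when neither is present. Prevalences cancel:

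- Event-free patients: OR = s^((h1 − 1)(h2 − 1)).
- Patients with the event: OR = (1 − s^(h1h2))(1 − s) / [(1 − s^h1)(1 − s^h2)].

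If either hazard ratio is 1, both odds ratios are exactly 1. With s = 0.8 (assumed):

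- h1 = h2 = 2: event-free 0.8^1 = 0.80; event (0.5904 × 0.20) / 0.36² = 0.91.
- h1 = h2 = 3: event-free 0.8^4 = 0.41; event (0.8658 × 0.20) / 0.488² = 0.73.

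**Step 4: what the Fisher tests would report.** In simulated trials of 32 patients with independent factors (each at 50% prevalence, 35–50% events), the chance of p < 0.05 in at least one of the two tables was:

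- 4.3–5.2% when neither or only one factor matters;
- 4.4–5.5% when both hazard ratios are equal, from 1.5 to 3;
- 7.1–9.1% when both are 5.

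One table in all 32 gave 3.1%.

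**Step 5: detecting a real overlap.** Simulated with prevalences 0.4 and 0.5 and a 20% base event risk, the chance of p < 0.05 was about:

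| True OR | HR of each factor | One table, all 32 | At least one of the two split tables |
|---|---|---|---|
| 8 | 2 | 69% | 46% |
| 8 | 3 | 69% | 25% |
| 4 | 2 | 35% | 21% |

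**The case against.** **The size of the loss is not known.** Stating that a third of the information is lost would need a normal covariate cut at its median. The baseline tables are empty shells, nothing says that 60 mL/min is central, and Cox information depends on events rather than on 32 patients. This objection stands, and the figures above are given as a range under assumptions.

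**The tables do not, in general, create a false association.** A reader might infer that conditioning on outcome makes two unrelated factors look linked. Step 3 shows that this needs both to be prognostic. Step 4 shows that the Fisher false-positive rate hardly moves for hazard ratios up to 3. What survives is narrower: the tables can distort or hide an association, and they split the patients.

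**The purpose of the tables is unstated.** They may be a check for sparse cells after a Cox fit, and the phrase about patients with EFS could mean event-free patients. A reader might also infer that Tables 125/126 were used to drop creatinine clearance from the reduced model in Table 127. That model also drops age, which these tables cannot explain, and no reduced model follows Tables 150/151 or 174/175. The documents do not establish such a step.

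**The cut at 71 is not shown to be data-derived.** It may look like a sample median, but no document says so, and nothing suggests it for 60. Labelling either cut data-derived would be unsupported.

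**Continuous terms have a cost.** Protocol section 4.1 allows clearance to be calculated by Cockcroft-Gault, whose formula contains age. The two terms would then be correlated by construction. This stands as a downside.

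**The section has a larger weakness:** seven covariates in 32 patients. That is true and this change does not cure it, but it is no reason to discard information as well.

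**Conclusion.** The point holds as a minor, inexpensive improvement. All four Cox tables use only unexplained splits at 71 years and 60 mL/min for variables collected as numbers. Under the assumptions in step 1, the loss is about 25% (uniform, median cut) to 36% (normal, median cut), rising to about half for a normal covariate cut 20/80. At an assumed 12 events and HR 2.0 per SD, power falls from 67% to 48% with a median split.

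The creatinine-ECOG tables are a secondary point and concern three endpoints, not OS. They do not answer whether the two factors overlap at baseline. They could understate a real overlap if both are prognostic, but the documents do not support the claim that they produce a false or wrong answer. The section is exploratory, and neither the primary endpoint nor the two-stage rule depends on it.

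**What to change.** 1. In Tables 124, 149, 173 and 197, and in any reduced model that retains them, enter age and creatinine clearance as continuous linear terms, reporting hazard ratios per 10 years and per 10 mL/min.
2. Keep the 71 and 60 splits for the Kaplan-Meier displays and state the reason for each cut. If no reason is on record, say so.
3. Replace Tables 125/126, 150/151 and 174/175 with one baseline table of creatinine clearance by ECOG in all 32 patients. If the paired tables serve another purpose, such as a sparse-cell check, state it and define which group each covers.

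The cost is analysis code and table shells only; no new data are needed. The downsides to record are the assumption of linearity on the log-hazard scale, and the correlation between the two terms where clearance is calculated by Cockcroft-Gault. The report should state which method was used for clearance.
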